9.5.6 Hepatic Monitoring

If a subject experiences elevated alanine aminotransferase (ALT) $\geq 3 \times$ upper limit of normal (ULN), alkaline phosphatase (ALP) $\geq 2 \times$ ULN, or elevated total bilirubin (TBL) $\geq 2 \times$ ULN, liver tests will be performed to confirm the abnormality.

The subjects' liver disease history and associated person liver disease history data will be listed. Any concomitant medication of acetaminophen/paracetamol will be listed. Results from any hepatic monitoring procedures, such as a magnetic resonance elastography (MRE) scan, and a biopsy assessment will be listed, if performed.

Hepatic risk factor assessment data will be listed. Liver related signs and symptoms data will be summarized by treatment and listed. Alcohol and recreational drug use data will also be listed.

All hepatic chemistry, hematology, coagulation, and serology data will be listed. Values outside the reference ranges will be flagged on the individual subject data listings.

9.5.7 Injection Site Local Tolerability Assessment Data

Injection-site assessment data will be listed and summarized in frequency tables by treatment, and timepoint.

9.5.8 Pain Measurements using the Visual Analog Scale (VAS)

Intensity of pain data at the injection site as soon as practicably possible after the injection, and at multiple postdose timepoints, as reported by the patient and measured according to the 0- to 100-mm VAS will be listed and summarized by treatment.

The time 0 (immediately after dosing) data will be analyzed, using the Wilcoxon signed-rank test. The difference in medians between LY900014 U-200 and LY900014 U-100 and the 90% CIs for the difference will be presented.

VAS data will also be summarized based on the following categories of score: 0, 1-10, 11-20, 21-30, 31-40, etc up to the maximum category by treatment and timepoint and also the categories ≤ 10 mm, ≤ 20 mm and ≤ 45 mm. The table will show number and percent of patients with observations in each category.

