#### **10.3.1.3. Statistical Evaluation of the Intensity of Injection-Site Pain**

Pain intensity will be assessed at each injection site immediately after the injection as reported by the subject and measured according to the 0- to 100-mm VAS.

A mixed-effect model will be used to analyze the time 0 (immediately after dosing) data using the statistical model that includes treatment, sequence, and period as fixed effects; and subject within sequence as a random effect. The distribution of the score data will be explored prior to analysis to determine whether data transformation is required. It is possible that VAS scores will be 0; hence if the distribution of the data implies that a log transformation is required, then the score may be updated to  $\log(\text{VAS}+1)$  to allow for the inclusion of the 0 values in the analysis.

Visual analog scale data will also be summarized based on the following categories of score: 0, 1 to 10, 11 to 20, 21 to 30, 31 to 40, etc., up to the maximum category by treatment and time point.

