3. INTRODUCTION

This SAP has been developed after review of the Clinical Study Protocol (final version dated 21 August 2017) and the version 1 SAP (dated 12 October 2017).

This SAP describes the planned analysis of the safety, tolerability, pharmacokinetic (PK) and pharmacodynamic (PD) data from this study. A detailed description of the planned TFLs to be presented in the clinical study report (CSR) is provided in the accompanying TFL shell document.

The intent of this document is to provide guidance for the statistical and PK analyses of data. In general, the analyses are based on information from the protocol, unless they have been modified by agreement between Eli Lilly and Company and Covance Early Clinical (EC) Biometrics. A limited amount of information concerning this study (e.g., objectives, study design) is given to help the reader's interpretation. This SAP must be signed off prior to first subject administration for this study. When the SAP and TFL shells are agreed upon and finalized, they will serve as the template for this study's CSR.

This SAP supersedes the statistical considerations identified in the protocol; where considerations are substantially different, they will be so identified. If additional analyses are required to supplement the planned analyses described in this SAP, they may be performed and will be identified in the CSR. Any substantial deviations from this SAP will be agreed upon between Eli Lilly and Company and Covance EC Biometrics and identified in the CSR. Any minor deviations from the TFLs may not be documented in the CSR.

This SAP is written with consideration of the recommendations outlined in the International Council on Harmonisation (ICH) E9 Guideline entitled Guidance for Industry: Statistical Principles for Clinical Trials¹ and the ICH E3 Guideline entitled Guidance for Industry: Structure and Content of Clinical Study Reports².

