9.3.2 Pharmacokinetic Statistical Inference

To compare PK parameters between LY900014 U-200 relative to LY900014 U-100, log-transformed AUC parameter estimates ($AUC[0-t_{last}]$, $AUC[0-\infty]$) and C_{max} will be analyzed using the mixed-effects model that includes treatment, sequence, and period as fixed effects and subject within sequence as a random effect. From the model, the difference in LSmeans and the corresponding 2-sided 90% CIs for the difference will be estimated and back-transformed from the log scale to provide estimates of the ratio of geometric LSmeans and 90% CI for the ratio of the LSmeans. Bioequivalence will be concluded if the 2-sided 90% CI is completely contained within the interval (0.80, 1.25).

Example **CCI** code:

```
proc mixed data=pk;
class patient period treatment sequence ;
model logpk = treatment period sequence / ddfm=kr alpha=0.1;
random patient(sequence);
lsmeans treatment;
run;
```

In addition, the same model without log transformation will be used for the analysis of the PK time parameters (early 50% t_{max} , and t_{max}). LSmeans, treatment differences in LSmeans, and the corresponding 90% CIs for the treatment differences will be estimated from the model. The treatment ratios and 90% CIs for the ratios will be calculated using Fieller's theorem. As a sensitivity analysis, the PK time parameters will be analyzed nonparametrically using Wilcoxon signed rank test.

In addition, the analyses described above will also be performed on the population of subjects who completed and had evaluable PK data in all study periods.

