9.4.2 Pharmacodynamic Statistical Inference

To address the secondary objective of comparing GD parameters (G_{tot} and R_{max}) between the LY900014 U-200 and LY900014 U-100 formulations, log-transformed G_{tot} and R_{max} estimates will be analyzed using the mixed-effects model that includes treatment, sequence, and period as fixed effects and subject within sequence as a random effect. From the model, the difference in LSmean estimates and the corresponding 90% for the difference will be estimated and back-transformed from the log scale to provide estimates of the ratios of geometric LSmeans and 90% for the ratio of the LSmeans. For GD parameters that have at least 1 patient with a value equal to zero, an analysis of original scale data (not log-transformed) will be performed as described below for the GD time parameters.

In addition, the same model without log transformation will be used for the analysis of the GD time parameters (tR_{max} and early 50% tR_{max}). LSmeans, treatment differences in LSmeans, and the corresponding 90% CIs for the treatment differences will be estimated from the model. The p-value for the difference between LSmeans will be used to determine statistical significance. The treatment ratios and 90% CIs for the ratios will be calculated using Fieller's theorem. Other GD time parameters may be analyzed in a similar manner. As a sensitivity analysis, the GD time parameters will be analyzed nonparametrically using Wilcoxon signed rank test.

In addition, the analyses described above will also be performed on the population of subjects who completed and had evaluable GD data in all study periods.

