11. CHANGES FROM THE PROTOCOL SPECIFIED STATISTICAL ANALYSES

The VAS statistical analysis was updated to a non-parametric analysis due to issues observed in ITSC.

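### The SAP's signed-rank test for injection pain drops the period adjustment; with balanced sequences this costs precision, not validity, and only if the first injection hurts much more than later ones

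*SAP*

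**What the plan says.** Protocol 10.3.1.3 analyses the time-0 VAS score with a "statistical model that includes treatment, sequence, and period as fixed effects; and subject within sequence as a random effect". It foresees awkward data ("It is possible that VAS scores will be 0") and allows a log transformation after adding 1.

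SAP 9.5.8 replaces this: "The time 0 (immediately after dosing) data will be analyzed, using the Wilcoxon signed-rank test". On estimation it adds: "The difference in medians between LY900014 U-200 and LY900014 U-100 and the 90% CIs for the difference will be presented". It names no period or sequence adjustment, and does not say how the two scores per formulation become one pair.

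SAP 11 declares the change: "The VAS statistical analysis was updated to a non-parametric analysis due to issues observed in ITSC". SAP 3 gives the SAP precedence: "This SAP supersedes the statistical considerations identified in the protocol; where considerations are substantially different, they will be so identified".

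The signed-rank test also appears in SAP 9.3.2 ("As a sensitivity analysis, the PK time parameters will be analyzed nonparametrically using Wilcoxon signed rank test") and SAP 9.4.2 ("As a sensitivity analysis, the GD time parameters will be analyzed nonparametrically using Wilcoxon signed rank test"). In both places the main model for those parameters keeps the period term.

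**The concern.** A signed-rank test on within-subject differences ignores the order in which the formulations were given. If the first injection hurts more than later ones, whichever formulation came first carries the extra pain. Each subject's difference is then pushed up or down according to sequence. The protocol's model would remove that push; the SAP's test leaves it in.

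Time-0 VAS is the only tolerability measure given a formal comparison of the two formulations. At stake is whether a real pain difference could be missed, or its interval be wider than the design requires. The declared reason concerns a move to a non-parametric method, and such a method can still use the randomised sequences.

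**Working it through.** **Inputs from the documents.** Four periods, each formulation given twice, about 44 completers. Example sequences (T = U-200, R = U-100): TRTR, RTRT, TRRT, RTTR. The 90% CI corresponds to a two-sided 10% level.

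**Assumptions.** The documents give no VAS standard deviation, treatment difference or period effect, so there is no stated figure to reproduce. Assumed: 11 subjects per sequence, within-subject SD sw = 8 mm, true difference 3 mm, an extra δ mm of pain in Period 1 only. The signed-rank test is assumed to be run on one contrast per subject, d = mean U-200 score minus mean U-100 score.

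**Step 1: where period effects go.** With period effects p1 to p4, d contains:
- TRTR and RTRT: plus and minus (p1 + p3 − p2 − p4)/2
- TRRT and RTTR: plus and minus (p1 + p4 − p2 − p3)/2

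A Period 1 effect therefore adds +δ/2 if U-200 came first and −δ/2 if U-100 came first. A sequence effect is constant within a subject and cancels in d, so omitting the sequence term costs complete subjects nothing.

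**Step 2: bias.** Expected shift = (δ/2) × (number with U-200 first − number with U-100 first)/N.
- 22:22: zero.
- 23:21: (1/2)(2/44) = 0.023δ.
- 24:20: (1/2)(4/44) = 0.045δ.
- 26:18: (1/2)(8/44) = 0.091δ, or about 1.4 mm for δ = 15 mm.

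**Step 3: noise with balanced sequences.** Without a period effect the variance of d is sw²/2 + sw²/2 = sw². The ±δ/2 adds δ²/4, so the inflation factor is 1 + δ²/(4sw²).

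| δ / sw | Variance factor | SE | 44 subjects act like |
|---|---|---|---|
| 0.5 | 1.06 | +3% | 41 |
| 1.0 | 1.25 | +12% | 35 |
| 1.5 | 1.56 | +25% | 28 |

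A steady decline of 9, 6, 3, 0 mm does little. It gives ±3 mm in the first pair of sequences ((9 + 3 − 6 − 0)/2) and 0 in the second ((9 + 0 − 6 − 3)/2). The added variance averages 4.5 against sw² = 64, about 7%.

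**Step 4: size and power.** These come from simulation with 3,000 to 4,000 runs per setting, with continuous scores and with integer scores floored at 0. The comparator is a rank test stratified by sequence pair.

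| Period 1 effect | Signed-rank power | Stratified rank power | Loss (points) |
|---|---|---|---|
| 0 mm | 74–77% | 74–76% | none; stratified test 1–3 lower |
| 4–5 mm | – | – | 0–2 |
| 8 mm | – | – | 5–6 |
| 10 mm | 60–66% | 72–76% | 10–12 |
| 15 mm | 46–53% | 71–76% | 23–26 |

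With no true difference and a 10 mm effect, the signed-rank test rejects in about 5% of runs instead of 10%; the stratified test stays near 10%. With completers split 13/9/13/9 (26:18) and a 15 mm effect, the signed-rank size rises to about 13%, against about 10% for the stratified test.

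**The case against.** A reader might infer that a first-injection effect shifts the estimated U-200 minus U-100 difference. With balanced sequences it does not (step 2). Replacement subjects take the sequence of the subject they replace, which tends to preserve balance. The 13/9/13/9 split is also unfavourable by choice: 13/9/9/13 gives 22:22 and no bias. What stands is that replacement is optional and the allocation ratio is not stated, so some imbalance is possible.

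A reader might also infer that the change was undeclared, or that it weakens the analysis compared with the protocol's model. SAP 11 declares it and gives a reason. On assumed skewed scores with many zeros, the signed-rank test had more power than a period-adjusted linear model on untransformed scores for δ = 0, 0.5 and 1 sw (64% v 51%, 62% v 53%, 56% v 51%), and less only at 1.5 sw (41% v 47%). Going non-parametric is therefore defensible. That argument does not cover dropping the period adjustment, because a stratified rank test keeps the advantage of ranks. On similar assumed scores its power was 75%, 73%, 70% and 66% for effects of 0, 0.5, 1 and 1.5 SD, against 75%, 73%, 66% and 51% for the signed-rank test.

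The strongest objection is that nothing in the documents points to a first-injection effect as large as one within-subject SD, and that VAS pain is not a primary, secondary or exploratory endpoint and carries no decision rule. Both parts stand, and they limit the weight of the point.

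**Conclusion.** The SAP's VAS test omits a period adjustment that the protocol had planned, and the stated reason does not require the omission. With balanced sequences the result is lost precision: a conservative test and an interval that is too wide. The loss is negligible for a Period 1 effect well below one within-subject SD, about 5 to 6 power points at one SD (8 mm), and 10 points or more from 10 mm upward. Bias needs uneven completion between U-200-first and U-100-first sequences, and at 26:18 it is about 0.09 times the effect. All of these sizes rest on assumed values, including the use of subject means.

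The documents do not support reading this as a threat to the PK or GD conclusions. There the signed-rank test is only a sensitivity analysis of exploratory time parameters, and the main models adjust for period. A disagreement between the two could partly reflect the missing period term, but its size was not examined for those parameters.

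Severity: consider.

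**What to change.** Keep the analysis non-parametric and use the randomisation:

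- Define each subject's contrast as mean U-200 score minus mean U-100 score at time 0. This also settles how two scores per formulation form a pair.
- Reverse its sign in the sequences that start with U-100. Compare each sequence with its mirror image by a rank-sum test, and combine the two pairs by the van Elteren method. Within a pair the period contrast is then the same on both sides and drops out, while the treatment difference appears doubled.
- Report half the stratified Hodges-Lehmann shift with its 90% CI as the treatment difference.
- Take the pairs from the actual randomisation schedule, because the sequence table is labelled as an example only.
- State a rule for subjects without all four scores; the signed-rank test needs one too.

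This can be the main VAS test or stand beside the signed-rank test. The same change is optional for the PK and GD time-parameter sensitivity analyses. The cost is SAP wording, a few lines of code, and about 1 to 3 power points if there is no period effect. SAP 9.5.12, which says no inferential safety analysis is planned, should be reconciled with 9.5.8 in the same edit.

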## 2. Schedule of Activities

Study Schedule Protocol I8B-MC-ITRQ

Procedure	Screening	Periods 1, 2, 3, 4			FU/EDa	Comments
	Up to Day -28	Day -1	Day 1	Day 2		
Informed consent	X					
Subject admission to CRU		X				
Enrollment		X				Applicable to Period 1 only.
Fasting	X	X				Subjects are expected to fast for approximately 8 hours before screening and at least 8 hours before each study drug dose (starting from the night of Day -1) until the end of the glucose clamp procedure (Day 1).
Physical examination	X				X	Physical examination at screening. Thereafter, targeted examination, as appropriate.
Medical assessment	X		Predose	X	X	Medical history at screening. Thereafter, medical assessments per Section 9.4.4.1.
Height	X					
Weight	X	X*			X	*Applicable to Period 1 only
Waist and hip circumference		X*				*Applicable to Period 1 only
Vital signs (supine)	X		Predose and 10 hours postdose (at the end of clamp procedure)		X	Vital signs: Body temperature, blood pressure, and pulse rate. Body temperature will be measured only at screening.
12-lead ECG	X	X			X	Single ECGs will be collected for safety.
Clinical laboratory tests	X		Predose of Period 1		X	See Appendix 2 , Clinical Laboratory Tests, for details.

Procedure	Screening	Periods 1, 2, 3, 4			FU/EDa	Comments
	Up to Day -28	Day -1	Day 1	Day 2		
Pregnancy test	X	X			X	For females of childbearing potential only. A serum pregnancy test will be performed at screening. Urine pregnancy tests at all other time points.
Study drug administration			0 hour			Time of study drug administration = 0 hour. Study drug will be administered at approximately the same times on Day 1 of each study period.
Injection-site assessments			0, 1, 4, and 10 hours postdose (at the end of clamp procedures)			Assessments of injection-site reaction at time '0' will occur immediately following injection of study drug.
Visual Analog Scale (VAS)			0, 20, and 60 min postdose			VAS assessment at time '0' will occur immediately following injection of study drug.
Insulin lispro PK sampling			0, 5, 10, 15, 20, 25, 30, 35, 40, 45, 50, 55, 60, 70, 90, 120, 150, 180, 240, 300, 360, 420, 480, 540, and 600 minutes			Sampling times are relative to the time of study treatment administration (time 0). Time 0 sample is to be collected immediately prior to injection.

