## 5.2. Number of Participants

Up to 60 subjects may be enrolled so that at least 44 subjects complete the study. For purposes of this study, a subject completes the study when all scheduled procedures shown in the Schedule of Activities (Section 2) have been completed.

If a subject discontinues from the study before completion of all 4 dosing periods, replacement subjects may be enrolled up to 60 subjects following agreement between the investigator and the sponsor.

The replacement subject will be assigned the treatment sequence of the discontinued subject and complete that sequence in its entirety.

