5. STUDY DESIGN

This is a Phase 1, single-center, investigator- and subject-blind, 4-sequence, 4-period, randomized, replicated-crossover, 10-hour euglycemic clamp study in healthy subjects to compare the PK and GD of insulin lispro in LY900014 U-200 formulation versus insulin lispro in LY900014 U-100 after SC administration of 15 U insulin lispro dose. The treatments will be replicated such that each formulation is administered twice on different occasions to healthy subjects over 4 study periods. Figure 1 illustrates the study design.

Abbreviation: CRU = clinical research unit

*Single dose of LY900014 U-200 or LY900014 U-100 administered subcutaneously to the abdomen

Figure 1. Illustration of study design

Each subject will be administered LY900014 U-200 formulation (on 2 occasions) and LY900014 U-100 formulation (on 2 occasions). Subjects will be randomly assigned to 1 of the 4 dosing sequences (Table 1).

Table 1. Treatment Sequence Example for I8B-MC-ITRQ

Treatment Sequence	Period 1	Period 2	Period 3	Period 4
1	LY900014 U-200	LY900014 U-100	LY900014 U-200	LY900014 U-100
2	LY900014 U-100	LY900014 U-200	LY900014 U-100	LY900014 U-200
3	LY900014 U-200	LY900014 U-100	LY900014 U-100	LY900014 U-200
4	LY900014 U-100	LY900014 U-200	LY900014 U-200	LY900014 U-100

Note: This is only an example table for illustration purpose; subjects will be assigned a treatment sequence according to the actual treatment randomization schedule provided to the unblinded site pharmacist.

Subjects will be required to attend the clinical research unit (CRU) on at least 6 occasions:

- 1 screening visit (may occur up to 28 days prior to randomization)
- 4 inpatient treatment visits for the clamp procedure (Periods 1 to 4) with a wash-out period of ≥ 3 days between discharge and the next admission to the CRU
- 1 follow-up visit (at least 14 days after the last dose).

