8. DEFINITION OF ANALYSIS POPULATIONS

The “Safety” population will consist of all subjects who received at least one dose of study drug, whether or not they completed all protocol requirements.

The “Pharmacokinetic” population will consist of all subjects who received at least one dose of study drug and have evaluable PK data.

The “Pharmacodynamic” population will consist of all subjects who received at least one dose of study drug and have evaluable PD data.

All protocol deviations that occur during the study will be considered for their severity/impact and will be taken into consideration when subjects are assigned to analysis populations.

Primary statistical analyses will be conducted on the set of subjects who complete at least the first period of treatment.

Supportive analyses will be done on the key parameters for the subjects who complete all treatment periods.

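### Does SAP 9.5.8 need to define its difference in medians, and the pairing of replicate VAS scores, before the time-0 pain analysis can be run?

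*SAP*

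**What the plan says.** SAP 9.5.8 (Pain Measurements using the Visual Analog Scale) states: "The time 0 (immediately after dosing) data will be analyzed, using the Wilcoxon signed-rank test". The next sentence gives the estimate: "The difference in medians between LY900014 U-200 and LY900014 U-100 and the 90% CIs for the difference will be presented". The section also plans tables of score categories by treatment and time point: "The table will show number and percent of patients with observations in each category".

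The design is replicated. SAP section 5 says that "each formulation is administered twice on different occasions to healthy subjects over 4 study periods", and the Schedule of Activities in Protocol section 2 sets VAS at "0, 20, and 60 min postdose" in each of Periods 1 to 4. A completer therefore has two time-0 scores on each formulation.

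Protocol 10.3.1.3 had planned a mixed model with treatment, sequence and period as fixed effects and subject within sequence as a random effect. It also warned of zeros: "It is possible that VAS scores will be 0". SAP section 11 records the move to a non-parametric analysis and attributes it to problems seen in another study. SAP section 3 says the SAP supersedes the protocol's statistical considerations.

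SAP 9.3.2 and 9.4.2 use the signed-rank test as a sensitivity analysis for the PK and GD time parameters. They give no pairing rule either.

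**The concern.** Three things look wrong.

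- **The estimate may not match the test.** Read literally, a difference in medians is the U-200 median minus the U-100 median, which ignores the crossover pairing. The estimate that belongs to the signed-rank test is Hodges-Lehmann, the median of all pairwise averages of the subject differences. The sample median of the paired differences is a third quantity.
- **The pairing is not stated.** The mixed model in the protocol took replicates as they came. The signed-rank test needs one difference per independent unit, and the SAP does not say whether the two scores are averaged, paired by occasion, or cut to one.
- **Incomplete subjects are not mentioned.** SAP section 8 says "Primary statistical analyses will be conducted on the set of subjects who complete at least the first period of treatment", and Protocol 5.2 says "Up to 60 subjects may be enrolled so that at least 44 subjects complete the study", which leaves room for 60 − 44 = 16 non-completers.

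Two statisticians could therefore get different numbers from the same text, and one reading could overstate the evidence. This is the SAP's only formal comparison of injection pain between the formulations.

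**Working it through.** The documents give no variance, effect size or power for VAS, so there is no planned figure to reproduce. Everything below is illustrative. Assumptions: 44 completers, between-subject SD 10 mm, within-subject SD 12 mm, two scores per formulation. A subject-by-formulation effect has SD s on each formulation.

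**1. Precision with continuous normal scores.** The difference of two-score means has variance 144/2 + 144/2 + 2s² = 144 + 2s². With s = 0:

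- Hodges-Lehmann: √[(π/3) × 144/44] = 1.85 mm (simulated 1.87).
- Median of the paired differences: simulated 2.25 mm. The large-sample variance ratio to Hodges-Lehmann is (π/2)/(π/3) = 1.5; simulated, (2.25/1.87)² = 1.4.
- Difference of the pooled medians: simulated 2.43 mm, and (2.43/1.87)² = 1.7.

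On such data the literal reading costs precision.

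**2. Precision with zeros.** The protocol expects zero scores. When the same scores are rounded and clipped at 0, the SDs under no treatment effect are:

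| Zero scores | Hodges-Lehmann | Median paired difference |
|---|---|---|
| about 41% | 1.13 mm | 0.84 mm |
| about 51% | 0.91 mm | 0.49 mm |
| about 61% | 0.64 mm | 0.20 mm |

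The order reverses. At 61% zeros the pooled-median difference (0.39 mm) also falls below Hodges-Lehmann. This does not make medians better, because their spread is small partly since they sit at 0. With a 5 mm shift on the underlying scale and 41% zeros, the averages are 3.1 mm (Hodges-Lehmann), 2.5 mm (median paired difference) and 5.0 mm (pooled medians). These are different quantities, so a variance ratio does not rank them.

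**3. False positives from the pairing.** The correlation between a subject's two paired differences is ρ = s²/(s² + 144). For s = 6 it is 36/180 = 0.2, and for s = 7.86 it is 61.8/205.8 = 0.3. Treating 88 pairs as independent gives a two-sided rejection rate at nominal 10% of 2 × [1 − Φ(1.645/√(1 + ρ))]:

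- ρ = 0: 10.0% (simulated 10.0%)
- ρ = 0.2: 13.3% (simulated 13.4%)
- ρ = 0.3: 14.9% (simulated 15.0%)

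With one difference per subject the simulated rate is 10.1%. A separate simulation with skewed, zero-heavy scores gave 10.3%, 13.1% and 15.7% for 88 pairs as subject-by-formulation variation rose, against 10.4%, 10.2% and 10.0% for one difference per subject.

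**4. Incomplete subjects.** A subject with no score on one formulation cannot enter a paired test, whatever the text says. In the example sequences (SAP Table 1) Periods 1 and 2 always contain both formulations, so anyone dosed in Period 2 has a score on each. What remains open is the subject with one score instead of two, where using the available score is the natural choice. If all 60 are dosed and 6, 5 and 5 leave after Periods 1, 2 and 3 (assumed), 60 − 6 = 54 enter the test. The SD of Hodges-Lehmann is then 1.76 mm, against 1.85 mm with completers only.

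**5. Would a named method remove the mismatch?** Not fully. If Hodges-Lehmann were specified with a test that ranks zeros by Pratt's method, its nominal 90% interval would cover about 93%, 95% and 97% at 40%, 50% and 60% zeros. It could still include 0 when the test falls below 10%.

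**The case for a change.** The strongest case for a change is that the choices alter the answer and the SAP created the gap itself. On one made-up set of 44 subjects with two replicates, averaging gave p = 0.022, 88 pairs gave p = 0.008, and the first replicate alone gave p = 0.156. The protocol's mixed model needed no pairing rule. The SAP replaced it without supplying one, and because the SAP supersedes the protocol, the older text cannot fill the space. A few words would settle it before any data are seen. Injection-site reactions are a named potential risk in Protocol 3.3, and tolerability is part of a secondary objective.

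The omission stands. The consequence largely does not. Two of those three p-values come from analyses an experienced analyst would not choose: one ignores the clustering within subject, the other discards half the data. No sentence in either document proposes them.

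SAP 9.5.12 says that no inferential safety analysis is planned. That cannot be used to play the point down, because 9.5.8 plainly plans a test and an interval. Since section 11 records the VAS analysis as a deliberate change, the sentence in 9.5.12 reads as general text left unadjusted. It is a clerical slip that does not alter what will be done.

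The table shells mentioned in SAP section 3 may hold the missing detail. They are not available, so nothing here relies on them.

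**Conclusion.** No change to the plan follows. SAP 9.5.8 leaves out a pairing rule and the name of an estimator and interval method, and 9.3.2 and 9.4.2 leave out the same pairing rule for sensitivity analyses. Analysts can fill both sensibly: one U-200 minus U-100 difference per subject from the mean of the available scores, and an estimate whose name is given with the result. If Hodges-Lehmann was meant, only its name is missing.

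The loss of precision (1.4 to 1.7 times the variance) holds for continuous scores only. At 41% to 61% zeros the median paired difference has the smaller null spread, so no estimator is shown to be superior for the data the protocol anticipates. Inflation to about 13% to 15% needs both an 88-pair analysis and a correlation of 0.2 to 0.3, and the documents neither show nor exclude that correlation.

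The stakes are low. VAS pain is not among the endpoints in Protocol Table ITRQ.1, no decision rule or power statement uses it, the category tables and the summaries by treatment will be produced on any reading, and the bioequivalence conclusion is untouched. All sizes rest on assumed SDs of 10 and 12 mm and assumed shares of zeros. The reasons for making no change do not depend on those exact values.
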